## Sedentary time and IHD

- Males and females
- Aged 18 years or above.
- Any ethnicity.

### **7.1.2 Exclusion criteria**

- Under 18 years of age.
- Unable to provide valid informed consent (lack of mental capacity).
- Not had a cardiac event diagnosed within the past 12 months.
- Unstable coronary disease.
- Disease or conditions with a prognosis of less than 6 months to end of life (palliative care).

## **7.2 Sampling**

### **7.2.1 Size of sample**

An estimated sample size was calculated using G\* Power (version 3.1.9.4). Based on previous data (Carson et al., 2014), it was estimated that 67 participants would be needed to detect a medium correlation coefficient ( $r$ ) of 0.3 between sedentary time and cardiac outcomes with 80% power at an alpha level of 5%. If drop out occurs, participants will be replaced to ensure minimum recruitment is met. This decision will be pragmatic in accordance with study timeline.

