**STUDY SUMMARY**

Study Title	Sedentary time in individuals with ischaemic heart disease and its association with cardiac function, structure and cardiovascular risk factors.
Internal ref. no. (or short title)	Sedentary time and cardiovascular risk factors in IHD
Study Design	Cross-sectional
Study Participants	Ischaemic heart disease patients
Planned Size of Sample (if applicable)	67
Follow up duration (if applicable)	7 days
Planned Study Period	7 days
Research Question/Aim(s)	What is the sedentary pattern of individuals with ischaemic heart disease and its association with cardiac function and cardiovascular risk factors?

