#### **4 RESEARCH QUESTION/AIM(S)**

- 1) How much time do individuals with ischaemic heart disease spend sitting per day?
- 2) What is the association of daily sitting with cardiac function, structure and cardiovascular risk factors in ischaemic heart disease?

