### **Data analyses**

Statistical analyses will be conducted using SPSS Version 28 (IBM, Armonk, NY, USA). Descriptive statistics will be reported as mean and standard deviation (SD). Data will be checked for normality across each category using quantile-quantile plots. Total sitting time, breaks in sitting, standing and light, moderate and vigorous intensity physical activity, and total number of sit to stand transitions (frequency of breaks) data will be presented as mean and SD and also expressed as a percentage of daily waking time.

Correlation coefficients will be used to explore relationships of sedentary time variables with cardiac and cardiovascular risk factors. Multiple regression analysis will be used to model each aforementioned independent variable separately with cardiovascular risk factors (blood pressure, BMI, waist circumference, anxiety and depression) and measures of cardiac function and structure. It will also be used to explore associations between sedentary time with cardiovascular risk factors and cardiac function and structure, adjusting for potential confounding variables, including type of condition, time since diagnosis of cardiac condition, age, gender, ethnicity, and socioeconomic status, and whether any measures are confounding variables to the association between sedentary time with cardiovascular risk factors and cardiac function and structure.

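### The sample size of 67 gives 80% power for r = 0.3 only with an undeclared one-sided test; two-sided, power is about 70% and 84 would be needed

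*Protocol*

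**What the plan says.** Section 7.2.1 states that "it was estimated that 67 participants would be needed to detect a medium correlation coefficient" "of 0.3 between sedentary time and cardiac outcomes with 80% power at an alpha level of 5" per cent. It names G*Power 3.1.9.4 as the software but gives neither the test nor the number of tails; on the error rate it says only "at an alpha level of 5" per cent. The Study Summary repeats 67 as the planned size. There is no inflation for dropout, because participants who drop out are to be replaced.

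The question the study is sized for is put without a direction. Section 4 asks: "What is the association of daily sitting with cardiac function, structure and cardiovascular risk factors in ischaemic heart disease". The second objective in section 4.1 is likewise to establish associations. The Data analyses part of section 5 says: "Correlation coefficients will be used to explore relationships of sedentary time variables with cardiac and cardiovascular risk factors". It then adds regression: "Multiple regression analysis will be used to model each aforementioned independent variable separately with cardiovascular risk factors", with further models adjusting for confounders, of which six are named.

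**The concern.** A size of 67 is smaller than expected for r = 0.3 at the usual two-sided 5% level, and it equals what a one-tailed calculation gives. If one tail was selected in the software and not reported, the protocol claims a power that the study lacks for the two-sided question it appears to ask.

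This matters because section 7.2.1 is the only justification for the size of the study, and the same figure serves as the minimum recruitment target. A reader who trusts the 80% would give a non-significant result more weight as evidence against a medium correlation than it can bear.

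**Working it through.** **Inputs, all from section 7.2.1:** n = 67, r = 0.3, power 80%, alpha 5%. The number of tails is not stated, so both cases were calculated.

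**Method.** The null hypothesis is a correlation of zero. The critical value is r_c = t / √(n − 2 + t²), where t is the quantile of the t distribution with n − 2 degrees of freedom at 1 − alpha (one-sided) or 1 − alpha/2 (two-sided). Power is the probability that the sample correlation passes r_c, from its exact distribution under bivariate normality with a true correlation of 0.3.

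**Step 1: reproduce the protocol's figure, one-sided 5%.** At n = 67, t = 1.669 and r_c = 1.669 / √(65 + 1.669²) = 0.203.

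| n | Power, one-sided |
|---|---|
| 66 | 79.8% |
| 67 | 80.3% |

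The smallest n reaching 80% is 67, the stated figure exactly.

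**Step 2: same inputs, two-sided 5%.** At n = 67, t = 1.997 and r_c = 1.997 / √(65 + 1.997²) = 0.240.

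| n | Power, two-sided |
|---|---|
| 67 | 70.4% |
| 83 | 79.6% |
| 84 | 80.03% |

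The smallest n reaching 80% is 84, which is 84 − 67 = 17 more than planned. A simulation of 100,000 samples of 67 gave 80.3% one-sided and 70.4% two-sided.

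**Step 3: check with Fisher's z.** n = ((z_alpha + z_power) / atanh(0.3))² + 3, with atanh(0.3) = 0.3095 and z_power = 0.8416.

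- One-sided: ((1.6449 + 0.8416) / 0.3095)² + 3 = 67.5, rounded up to 68.
- Two-sided: ((1.9600 + 0.8416) / 0.3095)² + 3 = 84.9, rounded up to 85.
- Two-sided power at 67: Φ(0.3095 × √64 − 1.9600) = Φ(0.516) = 69.7%.

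A noncentral-t model with a fixed predictor needs 64 one-sided and 82 two-sided, with 71.8% two-sided power at 67. No two-sided method comes near 67.

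**Step 4: what 67 does support, two-sided.** Power reaches 80% at r = 0.334. Alternatively, 80% power at r = 0.3 would need a two-sided alpha of about 9.8%.

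**Step 5: adjusted model (secondary; rests on assumptions).** The protocol does not give the partial correlation after adjustment or the number of covariate terms. Assume a partial r of 0.3 and k = 6 to 12 covariate degrees of freedom: six covariates are named, and several may have more than two categories. Using the exact test with n − k in place of n, two-sided power runs from 66% (k = 6) to 61% (k = 12). The fixed-regressor approximation gives about 71.5%, hardly below its 71.8% without covariates. The methods disagree on the cost of adjustment, but both stay below 80%.

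**The case against.** The strongest reply is that nothing in section 7.2.1 is arithmetically wrong as printed. All four figures agree under a one-sided 5% test, and the text never says two-sided. The background also leans one way: it reports detrimental associations of sedentary time with risk markers and a rise in blood pressure per sedentary hour. The number of tails used in the analysis is something a statistical analysis plan may settle, and that plan is not at hand. Finally, this is an exploratory cross-sectional study with no decision tied to one p-value, so a gap of 10 percentage points in power is a modest fault.

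Part of this stands:

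- The 80% claim is unsupported unless the test is one-sided; it is not impossible under every reading.
- That the expected signs differ between outcomes does not by itself rule out one-sided tests, since each outcome could have its own direction.
- The adjusted-model figures rest on assumed inputs, and sizing on an unadjusted correlation does match one of the planned analyses.
- The exploratory aim limits the consequences.

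It does not rescue the paragraph. The protocol neither declares nor justifies a direction, while its aims and analysis are worded neutrally. The background is mixed too: of 31 articles on blood pressure, 18 found no association. A later analysis plan with two-sided tests would confirm the shortfall. One with one-sided tests would still leave section 7.2.1 without the condition on which its figure depends, and at odds with the neutral aims.

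**Conclusion.** The concern holds. The planned 67 reproduces exactly with a one-sided 5% test and with no two-sided method tried. For the non-directional association that the protocol asks about, 67 participants give 70.4% power at r = 0.3, not 80%. The chance of missing such a correlation is 29.6%, about half as large again as the 20% implied (29.6 / 20 = 1.48).

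Two inferences carry this. That one tail was used is inferred from the exact match at 67. That two tails are meant is inferred from the neutral wording of the aims and analysis and from the usual reading of an unqualified 5% alpha. The figures assume bivariate normality and a single unadjusted correlation, and they allow nothing for multiple outcomes. The adjusted-model power is illustrative, and the conclusion does not depend on it.

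**What to change.** Rewrite the power statement in section 7.2.1 in one of three ways:

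1. **Keep 67 and restate the power.** Suggested wording: with a two-sided 5% test, 67 participants give 70% power to detect r = 0.30 and 80% power to detect r = 0.33; 84 would be required for 80% power at r = 0.30. This changes one paragraph and needs no extra participants; the cost is a less favourable stated power.
2. **Keep 80% power at r = 0.30 and raise the target to 84**, here and in the Study Summary. This costs 17 more participants with usable data.
3. **Declare a one-sided test**, give and justify the direction for each outcome, align the aims with it, and use the same test in the analysis.

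In each case, name the G*Power test and the number of tails. It would also help to state the power, or the detectable partial correlation, for the covariate-adjusted model, with the assumed number of covariate terms shown.

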##### **4.1 Objectives**

- 1) To identify daily sitting time in individuals with ischaemic heart disease in the first year of their cardiac recovery.
- 2) To establish objective associations of sitting time with cardiac function, structure and cardiovascular risk factors, including anxiety and depression.

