### *Cardiac function*

In a laboratory or in the participants home, the participant will be asked to undress from the waist up and lay on the medical couch in the left lateral decubitus position. Here, a scanning gel will be applied to the echocardiogram probe. This forms part of the echocardiogram system (Esoate, MyLab Omega, Italy). Parasternal and apical views will be acquired (Armstrong and Ryan., 2012). Once these images are collected and stored, the gel will be removed from the probe and chest. All images will be stored anonymously, where participants will be given a participant ID number. All image analysis will be completed using Echopac software (GE Healthcare, Version 113, GE healthcare, Chicago, Illinois, United States). Measures taken from the echocardiogram scan will be used to calculate left ventricular structure and function.

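### 67 participants give 80% power for r = 0.3 only in a one-sided 5% test that the protocol never states; a two-sided test has about 70%

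*Protocol*

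**What the plan says.** Protocol section 7.2.1 reports a G*Power calculation (version 3.1.9.4): "it was estimated that 67 participants would be needed to detect a medium correlation coefficient" of 0.3 "between sedentary time and cardiac outcomes with 80% power at an alpha level of 5" per cent. The relationship is described in no more detail than that. The number of tails is not given there or elsewhere in the protocol. The Study Summary repeats 67 as the planned size.

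The rest of the protocol expresses no direction. Section 4 asks what the association of daily sitting with the outcomes is. The second objective in section 4.1 reads "To establish objective associations of sitting time with cardiac function, structure and cardiovascular risk factors, including anxiety and depression". The Data analyses part of section 5 says "Correlation coefficients will be used to explore relationships of sedentary time variables with cardiac and cardiovascular risk factors", and then plans multiple regression, "adjusting for potential confounding variables, including type of condition, time since diagnosis of cardiac condition, age, gender, ethnicity, and socioeconomic status". On the cardiac side, section 5 says "Measures taken from the echocardiogram scan will be used to calculate left ventricular structure and function" and names no individual parameter.

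**The concern.** A power statement can be read only if the test behind it is known, and for a correlation that includes the number of tails. For the same r and the same nominal 5%, a one-sided test needs noticeably fewer participants than a two-sided one.

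Where alpha is quoted without qualification and the question is whether an association exists in either direction, a reader will normally assume two sides. If 67 came from a one-sided calculation, that reader credits the study with a 20% chance of missing a true correlation of 0.3, when the chance is nearer 30%. The consequence falls mainly on null results. A non-significant correlation between sitting time and a cardiac measure would be taken as stronger evidence against a medium-sized association than 67 participants can supply.

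**Working it through.** **Inputs.** From section 7.2.1: N = 67, r = 0.3, power 80%, alpha 5%. Assumed because not stated: null value r = 0, bivariate normal data, one correlation tested once. Normal quantiles: 1.645 (one-sided 5%), 1.960 (two-sided 5%), 0.842 (80% power). Fisher transform: atanh(0.3) = 0.3095.

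**Step 1: reproduce 67.** The Fisher z formula is n = ((z_alpha + z_power) / atanh(r))² + 3.

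- One-sided: ((1.645 + 0.842) / 0.3095)² + 3 = 67.5
- Two-sided: ((1.960 + 0.842) / 0.3095)² + 3 = 84.9

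Exact bivariate-normal power (noncentral t averaged over the distribution of the predictor's sum of squares) settles the rounding:

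| Test | N | Exact power |
|---|---|---|
| One-sided 5% | 66 | 79.8% |
| One-sided 5% | 67 | 80.3% |
| Two-sided 5% | 67 | 70.4% |
| Two-sided 5% | 83 | 79.6% |
| Two-sided 5% | 84 | 80.0% |

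So 67 is the smallest N that reaches 80% one-sided. The two-sided requirement is 84 (exact) or 85 (Fisher z, rounding 84.9 up).

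**Step 2: power at 67 by Fisher z.** Power = Φ(√(n − 3) × atanh(r) − z_alpha), and √64 × 0.3095 = 2.476.

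- One-sided: Φ(2.476 − 1.645) = Φ(0.831) = 79.7%
- Two-sided: Φ(2.476 − 1.960) = Φ(0.516) = 69.7%

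**Step 3: smallest r with 80% power at 67, two-sided.** By Fisher z, r = tanh((1.960 + 0.842) / 8) = tanh(0.350) = 0.337. The exact calculation gives 0.334.

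**Step 4: could another two-sided calculation give 67?**

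- A point-biserial (fixed-predictor) model with r = 0.3 needs 82 two-sided; its power at 67 is 71.8%. One-sided it needs 64.
- A regression F test with r² = 0.09 needs 82 with one predictor and 101 with two.
- A regression F test with f² = 0.15 needs 55 with one predictor, 68 with two and 77 with three. The 68 is close, but it is not 67, and it is not the correlation of 0.3 that section 7.2.1 describes.

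Of the calculations tried, only the one-sided correlation test yields 67.

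**The case against.** The strongest reply is that 67 is not an arithmetic error. It is correct for a one-sided 5% test, and the Background gives some reason to expect a direction, since it reports a detrimental association of sedentary time with risk markers in the general population. That much stands: the defect is a missing qualifier, and the 70% depends on a two-sided reading that the protocol does not state either. But the Background also reports that 18 of 31 articles found no association with blood pressure, and that no study appears to have examined cardiac function in this group. No directional hypothesis follows in the aims, objectives or analyses.

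A second reply is that the statistical analysis plan, which is not at hand, may settle the details. That is fair for the choice and ranking of echocardiographic measures and for how secondary associations are labelled. It is less persuasive for sidedness, because the sample size was fixed in section 7.2.1 and its stated power has no definite meaning without it.

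Three stronger readings are tempting and should be resisted.

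- **That the powered test cannot be identified.** Section 7.2.1 names a correlation coefficient, and the Data analyses part plans correlations, so the powered test is the unadjusted correlation. The adjusted regression is not separately powered, but the protocol does not claim that it is.
- **That the unnamed outcomes inflate the false-positive rate by a known amount.** The protocol does not say how many cardiac measures will be tested. It describes the analyses as exploratory and sets no rule for declaring significance, so any figure would rest on the reader's own counts.
- **That the study must enlarge to 84 or 85.** Nothing here requires that. The study can proceed at 67 with its power correctly described.

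**Conclusion.** The point holds in this limited form. The statement of 80% power at 5% alpha is true only for a one-sided test that the protocol neither declares nor justifies. Under the two-sided reading that its non-directional aims invite, it overstates power by about 10 percentage points. The chance of missing a true correlation of 0.3 is then about 30% against the 20% implied.

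This rests on a single Pearson-type correlation tested against zero in roughly bivariate normal data, with all 67 participants contributing. The protocol plans to replace dropouts, subject to the study timeline. The exact and Fisher z methods agree to within one percentage point. The first objective, describing daily sitting time, is unaffected.

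**What to change.** Amend section 7.2.1 in one of two ways.

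- **Two-sided at 5%:** keep 67 and state about 70% power for r = 0.3 or, equivalently, 80% power for r of about 0.33 to 0.34.
- **One-sided at 5%:** say so, give the direction and the reason for it, and keep 80% power for r = 0.3.

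In the same edit, name the cardiac measure to which the calculation refers, chosen by the investigators, and note that the figure applies to the unadjusted correlation and not to the confounder-adjusted regression. This is best done before outcome data are analysed, so that the choice of sidedness and measure cannot be influenced by the results.

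The cost is a few sentences of protocol wording, with no new data and no further recruitment. The downside is a less favourable stated power if the test is two-sided, or the burden of defending a one-sided test if it is not.

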### **7.2.2 Sampling technique**

Eligible patients will be approached during Phase 1 and 2 of Cardiac Rehabilitation or via advertisements (posters, social media posts, email). Convenience sampling will be used to ensure sufficient recruitment to the study.

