Sedentary behaviour is associated with cardiovascular risk markers in the general population. Within the US National Health and Nutrition Examination Survey (NHANES) survey, a detrimental linear association was found between total time spent sedentary and waist circumference, high density lipoprotein cholesterol (HDL-C), triglycerides, insulin, insulin sensitivity and  $\beta$  cell function (Healy et al., 2011). In addition, independent of total sitting time, a higher number of breaks in sitting per day was significantly beneficially associated with waist circumference, C-reactive protein and fasting plasma glucose (Healy et al., 2011). Therefore, both reducing total sedentary time and frequently breaking up prolonged periods of sedentary time are associated with improved cardiometabolic risk in the general population (Healy, et al., 2011). Further to this, a meta-analysis which reviewed the association between sedentary behaviour and blood pressure (BP) had somewhat varied findings (Lee & Wong, 2015). Of the 31 articles included, 18 articles found no association between sedentary behaviour and either systolic blood pressure (SBP) or diastolic blood pressure (DBP). Typically, those that did not find a significant association between SB and BP had a smaller sample size, and SB was objectively measured. Despite this, the subsequent meta-analysis (n=28) showed a significant association between SB and BP, of which every additional hour of SB per day was associated with an increase in 0.06 mmHg for SBP and 0.20 mmHg for DBP with an odds ratio of 1.02 (95% CI 1.00-1.03, p=0.02) for high blood pressure (both SBP and DBP). All studies adjusted for confounding variables, including age and sex, but some studies adjusted for more confounders than others (Lee & Wong, 2015). It is important to note that null findings were more prominent in studies that adjusted for moderate to vigorous physical activity, a historically known influence upon BP (Pescatello et al., 2004). However, these studies have typically been conducted in the general population, healthy individuals, or those who are overweight/ obese. There are currently limited studies that investigate the associations of sitting with cardiovascular risk factors in a population who have ischaemic heart disease. Furthermore, there appear to be no studies that have investigated the association of sitting time with cardiac function in this group, which is important to inform the potential importance of targeting reductions in sedentary behaviour as part of cardiac rehabilitation. Therefore, the aim of this study is to determine the prevalence of device measured sitting and the association of sitting with cardiovascular risk factors and cardiac function in individuals who have ischaemic heart disease.

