## **7.3 Recruitment**

### **7.3.1 Sample identification**

Participants will be identified by a member of the University research team who will regularly attend CR initial assessment telephone clinics. This member is also employed at Bedford Hospital as a Cardiac Rehabilitation Exercise Specialist. They will have access to the clinic list and medical notes prior to the consultation, where they can be screened to check who may be eligible for the study. This is usual practice as part of the role of a Cardiac Rehabilitation Exercise Specialist. All members of the research team involved in recruitment will have an NIHR research passport and will have completed secondary

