## Sedentary time and IHD

GCP (Cardiac Rehabilitation Exercise Specialist). Eligible patients will be approached by the Cardiac Rehabilitation Exercise Specialist to ask if they would be interested in volunteering to take part in the study via telephone.

Participants will be approached after their initial CR appointment by a member of the research team to invite them to take part in the study via telephone. An introduction to the study will be given and the patient will be sent a participant information sheet (PIS) either via email or post. A consent to contact form will be completed that allows the research team to call the patient to discuss the study further and explore whether they are interested in participating. It is optional and refusal to do so does not in any way affect their usual standard of care. If they complete a consent to contact form, the patient will be given at least 24 hours to read the PIS and discuss with friends and family, to carefully consider their participation in the study.

Participants will also be recruited using advertisements via recruitment posters, leaflets, emails, and social media.

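### Objective 1 describes sitting time in people with ischaemic heart disease, but the sample is by convenience although a clinic list is at hand, and nothing in the protocol would show who was left out

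*Protocol*

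**What the plan says.** The Background (section 1) closes by saying that "the aim of this study is to determine the prevalence of device measured sitting", together with its associations, in people with ischaemic heart disease. No cut-off for high sitting is defined, so prevalence here means the amount of daily sitting. Section 4 makes this the first research question, and section 4.1 the first objective: "To identify daily sitting time in individuals with ischaemic heart disease in the first year of their cardiac recovery".

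On sampling, section 7.2.2 says "Convenience sampling will be used to ensure sufficient recruitment to the study". Patients come from Phase 1 and 2 of cardiac rehabilitation or answer adverts. Recruitment is the only reason given for the method.

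On identification, section 7.3.1 describes a team member "who will regularly attend CR initial assessment telephone clinics", who is also the hospital's rehabilitation exercise specialist. On the list and notes it says: "They will have access to the clinic list and medical notes prior to the consultation, where they can be screened" for eligibility. The specialist then approaches eligible patients "to ask if they would be interested in volunteering to take part in the study via telephone". Posters, leaflets, emails and social media form a second route.

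The protocol describes no rule for the order or completeness of approach, no count of eligible, approached or declining patients, and no record of the route by which each participant came.

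**The concern.** A mean that is meant to describe a patient population depends on how people enter the sample. Convenience sampling leaves open who is approached, and both routes depend on people agreeing to join a study about sedentary time. If either step is related to how much people sit, the reported mean is shifted. A larger sample or replacement of drop-outs (section 7.2.1) would not reduce the shift, and the confidence interval would not reflect it.

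A better option is close at hand. For each attended clinic, the recruiter holds a list from which eligible patients can be counted. If they are not counted at screening, a later analysis plan cannot reliably rebuild the numbers, so this is a protocol matter and cannot be left to the SAP.

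**Working it through.** **1. The plan's own figure.** Section 7.2.1 gives 67 participants for r = 0.3, 80% power and alpha 5%. The exact test of a correlation gives n = 67 one-sided (power 80.3%) and n = 84 two-sided. The figure therefore reproduces on a one-sided basis that the text does not state; that is a separate matter. What counts here is that 67 was set for the correlation aim, not for estimating mean sitting time.

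**2. Sampling precision for objective 1.** Half-width of the 95% interval = t(66) × SD/√67 = 1.997 × SD/8.185 = 0.244 SD. The protocol gives no SD. Assuming 1.9 h/day, this is 0.244 × 1.9 = 0.46 h/day.

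**3. Shift from selection.** Let p be the share of eligible patients who take part. The population mean is p × (participants' mean) + (1 − p) × (non-participants' mean), so

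shift = (1 − p) × (participants' mean − non-participants' mean).

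The protocol gives neither input. Assume p from 30% to 70% and an absolute difference of 0.2 to 0.5 SD.

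| p | Difference (SD) | Shift (SD) | Actual coverage of nominal 95% interval |
|---|---|---|---|
| 0.7 | 0.2 | 0.06 | 92% |
| 0.5 | 0.35 | 0.175 | 70% |
| 0.5 | 0.5 | 0.25 | 47% |
| 0.3 | 0.5 | 0.35 | 18% |

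Coverage = Φ(1.96 − b√67) − Φ(−1.96 − b√67), with b the shift in SD. At SD 1.9 h, the range 0.06-0.35 SD is 0.11-0.67 h/day. The sign may be either, and a difference of zero gives no shift. For advert volunteers p cannot be defined, because the number of people reached is unknown.

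**4. Which part a consecutive approach removes.** Let a be the share of eligible patients approached and c the share of those who consent. The total shift splits into

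(1 − a) × (approached mean − not-approached mean) + (1 − c) × (consenting mean − refusing mean).

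Inviting everyone eligible sets a = 1 and removes the first term only. The second remains. The documents give nothing from which to divide the range in step 3 between the two terms.

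**5. Price of showing the estimate by route.** If half of the 67 come by each route, take n = 34: t(33) × 1.9/√34 = 2.035 × 1.9/5.831 = 0.66 h/day, against 0.46 h/day for the whole sample.

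**The case against.** The strongest reply is that the clinic route may already do what is asked. Section 7.3.1 says that eligible patients will be approached and names no selection among them; discretion is inferred mainly from the word convenience in section 7.2.2. If so, the change on that route is largely one of wording. That is possible, but the protocol does not commit to it, and the tally would still be missing.

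Second, the method is openly declared, in a PhD project without an external funder that was sized only for a correlation. This stands as a reason to keep the remedy cheap. It does not make the sample suited to objective 1.

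Third, section 5 notes that age, gender, diagnosis and intervention are routinely collected in rehabilitation, and comparisons may sit in an SAP that is not shown. The routine data make a tally easier, but the protocol does not provide for counting those who are not approached or who decline.

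A reader might also infer four stronger points that the documents do not support:

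- **That the team already screens the whole clinic list.** The text says only that patients can be screened, at clinics attended regularly.
- **That sitting time will be underestimated because active patients volunteer.** This is plausible, but nothing in the protocol fixes the direction.
- **That selection narrows the range of sitting and weakens the correlations in objective 2.** No figure supports this, and adverts could widen the range by reaching people outside the clinics.
- **That the shift in step 3 is what consecutive invitation would gain.** It measures all non-participation, including refusal, which remains.

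**Conclusion.** The point holds for objective 1. The protocol sets a descriptive aim, chooses a sampling method for recruitment reasons alone, and makes no stated use of the available clinic list to define or count the eligible group. Mean sitting time can be shifted in a direction and by an amount that the documents do not fix, and the protocol as shown collects nothing to detect it.

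The calculated range illustrates what could go unnoticed. It rests wholly on assumed participation and assumed differences, and it runs from negligible to larger than the sampling uncertainty. The study remains feasible and worth doing without the change. The change is still advisable because it is cheap and has to be in place before recruitment.

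**What to change.** - **Section 7.2.2, clinic route.** Replace convenience sampling by an invitation to every eligible patient on each attended clinic list until the target is met. The advert route can stay.
- **Section 7.3.1, tally.** Keep anonymous counts of eligible, approached, declined and enrolled patients by age band, sex, diagnosis and time since event, and report participants against them.
- **Recruitment route.** Record it for each participant. Beside the overall objective 1 estimate, show the estimate by route as a sensitivity description.

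This removes discretion in whom to approach and makes remaining selection visible on the tallied characteristics. It does not remove refusal bias or the restriction to rehabilitation contacts and advert responders, and the report should say so. If inviting every eligible patient proves impracticable, the tally and the route record are still worth having.

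The cost is revised wording, somewhat more invitations, and record-keeping alongside screening that the protocol already provides for. The sample size and measurements do not change. The by-route estimates will be less precise than the overall one, as shown in step 5 of the working, which is why they should accompany the overall estimate and not replace it.
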